## 3. STUDY DESIGN

### 3.1 Study Design

This is a prospective, randomized, sham-controlled, multi-center investigation designed for comparison of two parallel groups, gammaCore®-R (active treatment) and a sham (inactive) treatment. The study period will begin with a four week run-in period, during which there is no investigational treatment. The purpose of the run-in period will be to establish the baseline for comparisons. The run-in period will be followed by a 12 week randomized period when the subjects will be randomized (1:1) to either active treatment or sham (inactive) treatment. Figure 1 graphically displays the study design.

The randomized period will be followed by a 24 week open label period, where the subjects in the sham treatment group will switch treatment assignment and receive a gammaCore®-R device and the gammaCore®-R group will continue to receive an active treatment (See Protocol Section 7.1 for details).

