#### 7.4.2 Secondary Endpoints

##### *Percentage Reduction in Migraine Days and Responder Rate*

The percentage reduction in migraine days from the run-in period and achievement of 50% reduction in migraine days during the last 4 weeks of the randomized period are two secondary endpoints. Percentage reduction in migraine days is calculated as:

$$\text{Percentage Reduction} = -100 \times (\text{Change}_{\text{Run-in}} / \text{Run-in Value})$$

Using this value, an indicator of achievement of 50% reduction during the last 4 weeks of the randomized period can be defined as:

Response = 1 (Yes) if Percentage Reduction  $\geq 50\%$

Response = 0 (No) if Percentage Reduction is non-missing and  $< 50\%$

The number of migraine days, the change from run-in, and the percentage change from run-in to the open-label period will also be calculated. This will be completed for Month 3 and Month 6 of the OL period. For

$$\text{Month 3 OL Value} = \sum_{i=1}^{84} \text{Day } i, \text{ where Day } i = 1 \text{ (had a migraine)}$$

In the event that a subject does not have at least 70 days in the OL period the following rules will be used to calculate the Month 3 OL value:

1. If the number of study days in the OL period is less than 70, the month 3 OL value will not be calculated, but rather imputed to the DB value (and thus resulting in a  $\text{Change}_{\text{OL3}} = \text{Change}_{\text{Run-in}}$ , implying no change between the 3 month DB and 3 month OL periods).

$$\text{Month 3 OL Value} = \text{Month 3 (DB) Value}$$

2. If number of study days in the OL period is greater than or equal to 70, but less than 84, the month 3 OL value would be calculated as:

$$\text{Month 3 OL Value} = \sum_{i=1}^z \text{Day } i, \text{ where Day } i = 1 \text{ (had a migraine)}$$

where  $z$  represents the subject's last day (within 84 days) of participation in the OL period with diary data present.

To ensure consistency of this value for all subjects, the value will be adjusted to reflect an estimated number of days with migraine per 28 day interval. For example, if a subject records data for  $x$  days out of 28 days and have  $y$  days with migraine, then the adjusted number of days with migraine in 28 days is  $(28/x)*y$ , with a maximum value of 28.

Then the change from Run-in is calculated using the adjusted values as:

$$\text{Change}_{\text{OL3}} = \text{Month 3 OL value} - \text{Run-In value}$$

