$$\text{Month 6 OL Value} = \sum_{i=141}^{168} \text{Day } i, \text{ where Day } i = 1 \text{ (had a migraine)}$$

In the event that a subject does not have at least 154 days in the OL period the following rules will be used to calculate the Month 6 value:

1. If the number of study days in the OL period is less than 154, the month 6 OL value will not be calculated, but rather imputed to the Month 3 OL value (and thus resulting in a  $\text{Change}_{\text{OL6}} = \text{Change}_{\text{OL3}}$ , implying no change between the 6 month OL and 3 month OL periods).

$$\text{Month 6 OL Value} = \text{Month 3 OL Value}$$

2. If number of study days in the OL period is greater than or equal to 154, but less than 168, the month 6 OL value would be calculated as:

$$\text{Month 6 OL Value} = \sum_{i=1}^z \text{Day } i, \text{ where Day } i = 1 \text{ (had a migraine)}$$

where  $z$  represents the subject's last day of participation (within 168 days) in the OL period with diary data present.

To ensure consistency of this value for all subjects, the value will be adjusted to reflect an estimated number of days with migraine per 28 day interval. For example, if a subject records data for  $x$  days out of 28 days and have  $y$  days with migraine, then the adjusted number of days with migraine in 28 days is  $(28/x)*y$ , with a maximum value of 28.

Then the change from Run-in is calculated using the adjusted values as:

$$\text{Change}_{\text{OL6}} = \text{Month 6 OL value} - \text{Run-In value}$$

Results will be stratified by randomized treatment group.

In addition, the change from the double-blind period to 3 and 6 months of the open label period will be calculated or derived in the same manner for the comparison of the run-in to double-blind, randomized phase. Results will be stratified by randomized treatment group. For the calculation of percent change from the double-blind period to each of the open label periods, if there were zero migraine days at the double-blind period, percent reduction will be imputed as 100%.

$$\text{Change}_{\text{OL3DB}} = \text{Month 3 OL value} - \text{Month 3 value}$$

$$\text{Change}_{\text{OL6DB}} = \text{Month 6 OL value} - \text{Month 3 value}$$

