## 8.4.2 Secondary Efficacy Analyses

### Responder Rate

The number and percentage of subjects with at least a 50% reduction in migraine days will be summarized by device group, for each study phase (DB, 3 month OL, 6 month OL). The difference between the two device groups in will be compared using a two-sided, 95% CI (active minus sham). The p-value will be calculated using Fisher's exact test. If the p-value from the resulting exact test is <0.05, then the null hypothesis will be rejected.

As a sensitivity analysis, for responder rate in the DB phase, the two treatment groups will be compared using logistic regression analyses with an indicator for achieving at least a 50% reduction in migraine days (0 indicates no, 1 indicates Yes [event]) as the dependent variable and treatment group and center as fixed effects with number of migraine days in the 4-week run-in period as a covariate and again with treatment group, center, and aura as fixed effects with number of migraine days in the 4-week run-in period as a covariate.. The adjusted proportions, odds ratio, and 95% CIs f will be reported.

In addition, summary statistics and two-sided 95% CI will be produced for the following secondary effectiveness outcome measures and compared between the two treatment groups:

- The percentage reduction in migraine days during each time period (DB, 3 month OL, and 6 month OL) compared to the run-in period.
- The number of headache days during each time period (Run-in, DB, 3 month OL, and 6 month OL) as well as the change in number of headache days from the four week run-in period.
- The number of days in which acute headache medications were used during each time period (Run in, DB, 3 month OL, and 6 month OL); and, the change in the number of days from run-in.
- Scores at each visit and change in quality of life from run-in to each assessment as measured by the EQ-5D-5L, HIT-6, and MIDAS.

In addition, similar summaries may be produced for change in outcomes reported from the end of the DB period to assessments in the OL period.

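### Subjects with no migraine days in the double-blind period are scored as a 100% reduction in open label, although they can only stay at zero or get worse

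*SAP*

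**What the plan says.** SAP section 7.4.2, under the percentage-reduction heading, defines percentage reduction as -100 × (change / reference value), so a positive figure means improvement. The change from the double-blind period to OL Months 3 and 6 "will be calculated or derived in the same manner for the comparison of the run-in to double-blind, randomized phase". Two absolute measures follow: Change_OL3DB and Change_OL6DB, each the OL value minus the double-blind Month 3 value.

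The rule at issue covers only the percentages that take the double-blind value as their base, at both OL time points. It reads: "if there were zero migraine days at the double-blind period, percent reduction will be imputed as 100" per cent. It sets no condition on the OL value, and nothing elsewhere in the SAP qualifies it.

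Two carry-forward rules in the same section interact with it. With fewer than 70 OL days, the OL Month 3 value is set to the double-blind value, which the SAP describes as "implying no change between the 3 month DB and 3 month OL periods". With fewer than 154 OL days, the OL Month 6 value is set to the OL Month 3 value.

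On use, section 8.4.2 says that "similar summaries may be produced for change in outcomes reported from the end of the DB period to assessments in the OL period".

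**The concern.** A migraine-day value is a count, scaled to 28 days where needed, and cannot be negative. From a double-blind value of zero there is no room to improve, yet the rule gives the score that another subject earns only by falling from a positive count to zero. A relapse is recorded as complete success.

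What is at stake is how the DB-to-OL percent summary reads. It would show improvement where none occurred, and would disagree in direction with the absolute change for the same subjects. No net efficacy bias between the arms is claimed: in open label, section 3.1 says "the subjects in the sham treatment group will switch treatment assignment" and both groups use the active device. The effect is an upward shift in each arm's own summary.

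**Working it through.** **Inputs.** The formula, the zero rule, the two absolute changes and the carry-forward rules come from SAP section 7.4.2. The SAP does not give the share of subjects with a zero double-blind value (f) or the mean percent reduction in the others (m). Both are assumptions here, with f from 2% to 10% and m from +20% to -20%.

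**Where the 100% comes from.** Percent reduction = -100 × (OL - DB) / DB. At DB = 0 this is 0/0 if OL = 0, and a division by zero if OL > 0. The 100% is therefore a convention and not a result of the formula. For DB > 0, 100% is the ceiling and is reached only when OL = 0.

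**Individual cases.**

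| DB days | OL days | Absolute change | Percent reduction under the SAP |
|---|---|---|---|
| 0 | 0 | 0 | +100% (imputed) |
| 0 | 4 | +4 | +100% (imputed) |
| 0 | 5 | +5 | +100% (imputed) |
| 1 | 0 | -1 | -100 × (-1)/1 = +100% |
| 1 | 5 | +4 | -100 × 4/1 = -400% |
| 4 | 4 | 0 | -100 × 0/4 = 0% |
| 4 | 8 | +4 | -100 × 4/4 = -100% |

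The subject who rises by 5 days scores 500 points better than the one who rises by 4. Two subjects with no change score +100% and 0%.

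**Carry-forward.** Take a subject with DB = 0 and fewer than 70 OL days. OL Month 3 = DB = 0. Fewer than 70 days is also fewer than 154, so OL Month 6 = OL Month 3 = 0. Both absolute changes are 0, yet both percentages are +100%, and both OL values were carried forward.

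**Shift in an arm's mean**, compared with leaving these subjects undefined:

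- With the rule: (1 - f) × m + f × 100. Without it: m.
- Difference: f × (100 - m). Because m cannot exceed 100, the rule can never lower the mean.

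| f | m = +20% | m = 0% | m = -20% |
|---|---|---|---|
| 2% | 0.02 × 80 = 1.6 | 0.02 × 100 = 2.0 | 0.02 × 120 = 2.4 |
| 5% | 0.05 × 80 = 4.0 | 0.05 × 100 = 5.0 | 0.05 × 120 = 6.0 |
| 10% | 0.10 × 80 = 8.0 | 0.10 × 100 = 10.0 | 0.10 × 120 = 12.0 |

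Entries are percentage points and apply to each arm with its own f and m.

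**Shift in the median.** The imputed values sit at the top of the scale, so the overall median becomes the 0.5/(1 - f) quantile of the other subjects: 0.5/0.95 = 0.526 at f = 5% and 0.5/0.90 = 0.556 at f = 10%. The median moves less than the mean.

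**The case against.** **Reach.** Section 8.4.2 commits only to percentage reductions against run-in; the DB-to-OL summaries are optional and carry no named test. The matching secondary objective in section 2.2 concerns the number of days, which the absolute change already answers. This stands and keeps the point small. It does not remove it: section 7.4.2 says the DB-to-OL change will be calculated, and a percent summary produced as specified would be wrong.

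**The 0-to-0 case.** Anyone with a positive double-blind value who is migraine-free in open label scores 100%, so giving 100% to a subject who stays at zero is a recognisable way to credit continued freedom from migraine. As a status label that is arguable. As a measure of change from double-blind it fails, because nothing was reduced; any reduction from run-in is already captured by the run-in-based percentages. The rule also does not require OL = 0, so relapse earns the same credit.

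**Carry-forward.** The early-dropout example is the 0-to-0 case reached by imputation. That is fair: it illustrates the same error and is not a second one.

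**Size.** Both f and m are assumed, and small denominators can push m well below -20%, as the -400% case shows. The comparison is between two conventions, and leaving subjects out is not neutral either. All of this stands, so the point figures are illustrations and not bounds or estimates of bias.

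**Conclusion.** The rule is wrong as written. It gives the maximum improvement score to every subject with a zero double-blind value, none of whom can improve, and it contradicts the absolute changes defined beside it. That conclusion needs no assumption beyond counts being non-negative. The clearest error is OL > 0, where worsening is recorded as a 100% reduction; the 0-to-0 case is also wrong as a measure of change.

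The size depends on assumed f and m: about 2 points on an arm's mean at f = 2%, and 8 to 12 points at f = 10%, for m between +20% and -20%. The consequence is confined to the DB-to-OL percent summary. The primary endpoint, the responder rate, the run-in-based percentages and the absolute changes do not depend on it. It should be corrected, but no main conclusion of the trial rests on it.

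**What to change.** Delete the 100% imputation from section 7.4.2 and name Change_OL3DB and Change_OL6DB as the DB-to-OL measures. If the percent change is kept:

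- leave it undefined when the double-blind value is zero;
- state that the percent summary excludes these subjects;
- report by arm, at OL Month 3 and OL Month 6, how many of them stayed at zero and how many rose above zero.

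The counts are essential, because the exclusion removes exactly those who can only stay the same or worsen. A smaller repair, withholding the 100% only when OL > 0, would remove the worst error but would still score a 0-to-0 subject as a full reduction.

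The cost is SAP wording and, if the percentage is kept, one small count table. The zero-value subjects remain in the absolute-change summary.

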#### *Headache Days and Headache Medications*

Change from run-in to the last 4 weeks of the randomized period in the number of headache days (as opposed to migraine days) is another secondary endpoint and will be calculated in the same manner as the primary endpoint.

The number of days in which acute headache medications were used; and, the change in the number of days from run-in to the last 4 weeks of the randomized period are also secondary endpoints. Similar to the primary endpoint, an indicator of acute headache medication usage is collected in the e-diary and the number of days of usage and the change in the number of days from run-in to the last 4 weeks of the randomized period will be calculated in the same manner as the primary endpoint. In addition, the number of days in which 1) simple analgesics (aspirin, paracetamol, ibuprofen, NSAIDs), 2) triptans and ergots, 3) combined analgesics, and 4) opioids were used, and the change in number of days from run-in to the last 4 weeks of the randomized period will be analyzed similarly.

#### *MIDAS*

The total score on the MIDAS is captured on the eCRF, but will be recalculated for analysis as the sum of the response to the questions. Should any question be blank or unanswered, no total score will be calculated. The MIDAS eCRF will be completed at V2 (the end of the run-in period), V6 (the end of the

randomized period), V10 (12 weeks following the start of the OL period), and at V12 (24 weeks following the start of the OL period). The change in the MIDAS total score from the run-in period to each assessment will be calculated. Change in MIDAS total score may also be calculated from the end of the DB period to each assessment in the OL period.

The level of disability on the MIDAS, is defined using the total score as:

0 to 5	MIDAS Grade I, Little or no disability
6 to 10	MIDAS Grade II, Mild disability
11 to 20	MIDAS Grade III, Moderate disability
21+	MIDAS Grade IV, Severe disability

#### *HIT-6*

The total score on the HIT-6 is captured on the eCRF, but will be recalculated for analysis as the sum of the response to the questions. Should any question be blank or unanswered, no total score will be calculated. The HIT-6 eCRF will be completed at V2 (the end of the run-in period), V4, V5, V6 (the end of the randomized period), V8, V9, V10 (12 weeks following the start of the OL period), and at V12 (24 weeks following the start of the OL period). The change in the HIT-6 total score from the run-in period to each assessment will be calculated. Change in HIT-6 total score may also be calculated from the end of the DB period to each assessment in the OL period.

#### *EQ-5D-5L*

The EQ-5D is a generic, preference-based health utility measure with questions about mobility, self-care, usual activities, pain/discomfort, and anxiety/depression that are used to build a composite of the subject's health status. Each question is scored as 1 for no problem, 2 as slight problems, 3 as moderate problems, 4 as severe problems, and 5 indicating extreme problem. Ambiguous values (eg. 2 boxes are ticked for a single dimension) will be treated as missing (neither value used).

The 5 scores will then be converted into a single summary index by using the EQ-5D-5L Index Value Calculator tool (<http://www.euroqol.org/about-eq-5d/valuation-of-eq-5d/eq-5d-5l-value-sets.html#c655>, last accessed 18-Jan-2016) published by the EuroQol group. If any of the 5 scores are missing, the summary index will not be calculated and set to missing.

The second component of the EQ-5D is a visual analogue scale (VAS), asking subjects to rate their health from 0 to 100 where 0 represents the worst imaginable health state and 100 represents the best imaginable health state.

The EQ-5D will be completed at V2 (the end of the run-in period), V4, V5, V6 (the end of the randomized period), V8, V9, V10 (12 weeks following the start of the OL period), and at V12 (24 weeks following the start of the OL period). The change in the EQ-5D total score and change in the EQ-5D VAS from the run-in period to each assessment will be calculated. Change in EQ-5D total score and change in the EQ-5D VAS may also be calculated from the end of the DB period to each assessment in the OL period.

### *Other Endpoints*

The study subject will complete blinding questionnaires at 1-week (V3) into the randomized period and at the completion of randomized period (V6) as part of the data collection requirements. The blinding questionnaire asks subjects which treatment they think they received (“Active Stimulation”, “Sham Control”, or “Don’t know”).

## 7.5 Safety

Common safety variables include the following:

- Extent of Device Usage
- Adverse events
- Concomitant medications/treatments
- Vital signs

### 7.5.1 Extent of Device Usage

Administration of the 2 stimulations in the morning, midday and evening is collected in the e-diary as well as the number of stimulations if different from the planned number. In addition, dispensing and return of dispensed devices is recorded in the eCRF.

Extent of device usage will be defined as the percentage of days a subject used the device. Extent of device usage will be presented for each four week interval.

Compliance with device usage will be computed as the percentage of expected stimulations actually administered. The number of expected stimulations is determined for **each four week interval** as:

28 days x 3 times per day x 2 stimulations each time = 168 expected stimulations per month

If there are fewer than 28 days in a time period then the number would be modified accordingly.

The actual number of stimulations actually administered is calculated as the sum of the actual administrations for the same time interval as for the expected stimulations.

Compliance is then calculated as the actual number administered / expected number administered and multiplied by 100 to obtain the percentage.

Compliance will be then categorized into groups according to full compliance: 100%, 67%<100%, 33%<67% and <33%.

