### 5.2 Per Protocol (PP) Population

The per protocol (PP) population includes all ITT subjects who received the correct treatment with no major protocol deviations which could affect the assessment of efficacy. Major protocol deviations include, but are not limited to, the following:

- The subject did not reach visit 6
- Less than 67% compliance with treatment per month in the randomized period (refer to section 6.3).

The final criteria for the PP population, regarding which protocol deviations warrant exclusions, will be determined when all data on protocol deviations are available and before breaking the blind.

If the difference in sample size between the ITT and PP populations is more than 5%, then the primary efficacy analyses will be repeated in the PP population.

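### Compliance is an uncapped total of stimulations over the number expected, so stimulations above plan can offset untreated days, and a total above 168 falls in no compliance category

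*SAP*

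**What the plan says.** Section 7.5.1 sets the expected number for a four-week interval: "28 days x 3 times per day x 2 stimulations each time = 168 expected stimulations per month". The number is reduced when the interval is shorter. The e-diary records the morning, midday and evening administrations, "as well as the number of stimulations if different from the planned number". For the numerator, the section states: "The actual number of stimulations actually administered is calculated as the sum of the actual administrations for the same time interval as for the expected". The ratio follows: "Compliance is then calculated as the actual number administered / expected number administered and multiplied by 100 to obtain the percentage". The result is grouped: "Compliance will be then categorized into groups according to full compliance: 100%, 67%<100%, 33%<67% and <33" percent.

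The same section has a second, day-based measure: "Extent of device usage will be defined as the percentage of days a subject used the device". It is presented for each four-week interval.

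Section 5.2 uses compliance to define the per-protocol (PP) population. Its list of major deviations begins "Major protocol deviations include, but are not limited to, the following" and includes "Less than 67% compliance with treatment per month in the randomized period (refer to section 6.3"). Section 6.3 only defines the 28-day months, so the compliance formula has to be taken from section 7.5.1. Section 5.2 sets no upper limit and does not use the day-based measure.

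**The concern.** The description, the categories and the formula in section 7.5.1 do not fit together. The description and the categories imply a quantity that cannot exceed 100%. The formula can exceed it, because the diary allows for counts that differ from plan and nothing caps the sum per session, per day or in total.

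There are two consequences. First, a surplus on some days cancels a deficit on others, so the ratio can be at or near 100% for a subject who left the device unused on a number of days. The 67% limit in section 5.2 inherits this. Second, a subject whose total exceeds the expected number belongs to none of the four groups. The programmer must then decide whether to drop such subjects from the table or to read the top group as 100% or more. The SAP settles neither.

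At stake are the categorised compliance table and the make-up of the PP population, which is meant to hold subjects treated as planned.

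**Working it through.** **Inputs.** From section 7.5.1: 3 sessions a day, 2 stimulations each, 28 days, and an uncapped sum as numerator. From section 5.2: the PP limit of 67% per month. The daily counts of 8 and 12 below are illustrative assumptions and do not come from the SAP.

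**The plan's own figure.** 28 × 3 × 2 = 168, or 6 per day. This reproduces.

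**Formulas.**
- As written: 100 × (sum of daily counts) / 168.
- Capped at plan: 100 × (sum of the smaller of the daily count and 6) / 168.

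**Offsetting.**

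| Pattern over 28 days | Total | As written | Capped at 6 per day | Days used |
|---|---|---|---|---|
| 28 days at 6 | 168 | 100.0% | 100.0% | 100.0% |
| 21 days at 8, 7 at 0 | 168 | 100.0% | 126/168 = 75.0% | 75.0% |
| 14 days at 12, 14 at 0 | 168 | 100.0% | 84/168 = 50.0% | 50.0% |
| 15 days at 8, 13 at 0 | 120 | 71.4% | 90/168 = 53.6% | 53.6% |
| 10 days at 12, 18 at 0 | 120 | 71.4% | 60/168 = 35.7% | 35.7% |
| 28 days at 8 | 224 | 133.3% | 100.0% | 100.0% |

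**PP limit.** 0.67 × 168 = 112.56, so 113 stimulations are needed. At the planned 6 per day this takes 19 days (19 × 6 = 114, 67.9%), since 18 days give 108 (64.3%). At 8 per day 15 days suffice, and at 12 per day 10 days. Because the limit applies to each month, such a pattern must recur every month for the subject to stay in the PP population.

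**Category gap.** This needs no unusual pattern: 169/168 = 100.6% already falls outside all four groups.

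**Limit of a cap alone.** In the last row of the table the cap turns 133.3% into 100.0% and hides the over-use. A cap therefore needs a separate count of totals above 100%.

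**Session or day.** The capped column uses a daily cap. A per-session cap at 2 gives the same result when every session on a treated day reaches 2, and a lower one when some sessions are missed.

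**The case against.** Several points on the other side stand.

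- Gaps are not invisible. The percentage of days used is reported for each four-week interval and would show the most extreme pattern above as 35.7%.
- Over-use does not vanish. Section 8.5.1 summarises compliance descriptively, and section 8.1 includes the maximum, so a value of 133.3% would appear there. Only the grouped table has a gap.
- The PP criteria remain open until just before unblinding, so erratic or excess use could still be made an exclusion.
- The 67% limit applies per month, so one irregular month at double use does not decide the matter.
- The diary wording shows that counts may differ from plan. It does not show that counts above plan occur, or that the device permits them.
- Little depends on the measure. Section 5.2 repeats only the primary efficacy analyses in the PP population, and only if it differs from ITT by more than 5%. The adverse event tables in section 8.5.2 do not use the compliance groups.

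One could add that actual over expected is an ordinary definition of compliance, and that a cap is a preference. This is weaker: section 7.5.1 itself describes a share of the expected stimulations and gives groups that stop at 100%, and its formula delivers neither. The open PP list does not remove the problem either, because it leaves open which deviations exclude a subject, while the compliance formula is fixed.

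**Conclusion.** The point holds in a limited form. The formula in section 7.5.1 does not produce the quantity that the section describes and groups. Surplus stimulations can offset untreated days, by 25 percentage points in the 21-day example and 35.7 in the 10-day example, and any total above 168 has no category.

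The effect is confined to the categorised compliance table and the PP repeat of the primary analysis. That repeat could well be run: the SAP plans for 15% drop-out, not reaching visit 6 is a PP exclusion, and the trigger is a 5% difference. The ITT primary analysis is untouched.

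A reader might infer more than the document supports. One inference is that over-users are labelled fully compliant. As written, a total above 100% is unclassified. The top label applies only where over- and under-use net to exactly the expected number, or where a programmer reads 100% as at least 100%. Another is that the PP population will be contaminated or that exposure data are lost. The SAP gives no frequency of over-use, the patterns above are assumed, and the day-based measure and the descriptive maximum keep the information available.

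**What to change.** In section 7.5.1, for the compliance groups and for the section 5.2 criterion, count stimulations only up to the number that the SAP already plans for each session. Section 7.5.1 does not say whether differing counts are recorded per session or per day. If only daily counts exist, apply the cap per day. In shorter intervals, use the same reduced number of expected stimulations as now. Refer to section 7.5.1 in the section 5.2 criterion, so that the formula behind the 67% limit is explicit.

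Report total stimulations separately, by device group and period, with an explicit row for totals above 100% of expected. Both parts are needed, since the cap alone would hide over-use. This changes only how use is measured and tabulated, not the regimen.

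The cost is a few sentences in the SAP and one extra table row, with no new data if the diary counts are as described. Compliance figures may look slightly less favourable and the PP population may be slightly smaller. The change should be made before the PP decisions and unblinding.
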